2.2. Sample Size and Power Considerations

To demonstrate the noninferiority of the Praluent 75 mg Q2W/up-titrate 150mg Q2W dose regimen relative to placebo for the primary endpoint of mean change in Spatial Working Memory (SWM) strategy z-score from baseline to week 96, the sample size for this study is calculated to be 1085 patients per treatment group. This sample size is based on the noninferiority margin of 0.2 for the primary outcome measure. Specifically, a worsening in the SWM strategy z-score of 0 to 0.2 at the group level (small effect size) would not be considered clinically meaningful. Whereas a worsening of 0.3 to 0.5 (or greater), a small-to-medium effect size, might be considered clinically relevant, indicating increased cognitive impairment (Roiser 2015). Therefore, a noninferiority margin of 0.2 on the SWM strategy z-score change from baseline is a conservative estimate of the largest clinically meaningless mean difference between Praluent and placebo treatment groups. Additionally, the assumed mean difference between the treatment groups is 0 and the standard deviation is 1.0 (the standard deviation is obtained from the Cambridge Cognition internal normative data). To achieve 95% power using a 2-sided 95% confidence interval (CI) approach (2-sided alpha=0.05), the sample size is calculated to require 651 patients per treatment group. Assuming dropout rate of 20% in the first year and 25% in the second year, the sample size is increased to 1085 patients per treatment group.

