4.6. Primary and Secondary Endpoints

4.6.1. Primary Neurocognitive Endpoint

The primary outcome measure is the change in CANTAB cognitive domain SWM strategy score (SWMS) from baseline to week 96. Two definitions will be provided for this endpoint, specifically:

- SWM strategy z-score change from baseline is defined for each patient as: week 96 SWM strategy z-score minus the patient's baseline SWM strategy z-score. The change from baseline SWM strategy z-score is used for the primary analysis evaluation of noninferiority. A lower score denotes better SWM function (ie, less impairment).
 - A patient's SWM strategy z-score at week 96 is defined as: (week 96 SWM strategy raw score minus the SWM strategy mean baseline score) divided by the SWM strategy baseline standard deviation. The SWM strategy mean baseline score and the SWM strategy baseline standard deviation are calculated using patients in both treatment groups (ie, Praluent and placebo).
 - The SWM strategy z-score at baseline is defined for each patient in the same manner as the calculation for the SWM strategy z-score at week 96, replacing the patient's week 96 raw score with the patient's baseline raw score.
- SWM strategy raw score change from baseline is defined for each patient as: week 96 SWM strategy raw score minus the patient's SWM strategy baseline score. The SWM strategy raw score change from baseline is provided descriptively for clinical interpretation of function at week 96. Lower change from baseline raw scores reflect better SWM performance (ie, less impairment).

The baseline SWM strategy score is the last score obtained before the first dose of study treatment. The SWM Strategy score at week 96 is the score obtained within the week 96 analysis window and during the treatment-emergent adverse event (TEAE) period. The TEAE period is defined as the time from the first double-blind study treatment injection up to 70 days after the last double-blind study treatment injection. The analysis window used to allocate a time point to a measurement is defined in Appendix 10.2 of this SAP.

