5.6. Analyses of Primary and Secondary Endpoints

5.6.1. Analyses of Primary Neurocognitive Variable

The primary neurocognitive analysis is a statistical evaluation of the noninferiority of the Praluent 75 mg Q2W/up-titrate 150 mg Q2W dose regimen to placebo for the primary endpoint of change in SWM strategy z-score from baseline to week 96 in the primary safety population. The 2-sided 95% CI for the mean treatment difference at week 96 will be determined using an appropriate contrast statement in a mixed-effect model with repeated measures (MMRM). The upper CI limit will be compared to the noninferiority margin which is defined as 0.2 and the noninferiority will be declared if the upper CI limit is below the noninferiority margin.

In the case noninferiority is achieved for the primary neurocognitive function endpoint comparison, superiority of the primary neurocognitive function endpoint will be assessed using the same upper CI limit calculated for the primary comparison. Specifically, the upper CI limit will be compared to zero and superiority will be declared if the upper CI limit is below zero. A statistical multiplicity adjustment is not needed, since this process of noninferiority achievement followed by superiority assessment using the same 95% upper CI limit on the primary endpoint corresponds to a simple closed test procedure (EMA/CPMP/EWP/482/99 – 27July 2000).

The MMRM model will include the fixed categorical effects of treatment group (placebo, Praluent), both randomization strata (as per IVRS/IWRS), time point (weeks 24, 48, 72, and 96), treatment-by-time point interaction, and strata-by-time point interaction, as well as the continuous covariate of baseline SWM strategy raw score value and baseline value-by-time point interaction. Post-baseline assessments within a patient's TEAE period will be included in the analysis and missing data are accounted for by the MMRM model. Model assumptions for normality will be explored prior to the analysis testing.

This model will be run using Statistical Analysis Software (SAS) mixed procedure with an unstructured correlation matrix to model the within-patient errors. Parameters will be estimated using restricted maximum likelihood method with the Newton-Raphson algorithm. Denominator degrees of freedom will be estimated using Satterthwaite's approximation.

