5.6.1.2. Sensitivity to the Handling of Missing Data

Sensitivity analyses will be conducted to assess the robustness of primary analysis with regards to handling of missing data (3).

Visual examination:

- In order to explore the missing data pattern, post-baseline SWM strategy z-score observations during the TEAE period (in the primary safety population) will be described according to the following groups:
 - SWM strategy z-score available at week 96 (i.e. primary endpoint available),
 - SWM strategy z-score available at week 72 but missing at week 96,
 - SWM strategy z-score available at week 48 but missing from week 72,
 - SWM strategy z-score available at week 24 but missing from week 48,
 - SWM strategy z-score missing from week 24.

A graph of mean SWM strategy z-score (respectively change from baseline in SWM strategy z-score) \pm SE at baseline, and weeks 8, 12, 24, 48, 72, and week 96 will be provided by missing data pattern, for each treatment group.

- In the primary safety population, demographic and baseline characteristics will be described within the missing data pattern number 1 versus the pooled others. P-values from Chi-square test for categorical data and from asymptotic one-way ANOVA test for Wilcoxon scores (Kruskal-Wallis test) for continuous data, will be also provided, for descriptive purposes.

Multiple Imputations:

In addition to the MMRM method, the multiple imputation method (see Appendix 10.5 for more details) will be used to address missing values, in the primary safety population, followed by the testing of treatment arms using an analysis of covariance (ANCOVA) model, with the intent to evaluate the robustness of the primary analysis using a different statistical method.

Missing data from the primary safety population will be imputed 100 times to generate 100 complete data sets, using the MI SAS procedure (using Markov Chain Monte Carlo). The

percent change from baseline at week 96 will be then derived from observed and imputed SWM strategy z-score at this time point. The 100 complete data sets will be then analyzed using an ANCOVA model with treatment group and randomization strata (as per IVRS/IWRS) as fixed effects, and the baseline SWM strategy z-score as continuous covariate, and the MIANALYZE procedure will be used to generate valid statistical inferences by combining results from the 100 analyses using Rubin's formulae (4).

Pattern mixture model:

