The MMRM model relies on the “missing-at-random” (MAR) assumption. Because the possibility for a not-missing-at-random (NMAR) missingness mechanism can never be excluded, sensitivity analysis to explore the impact of non-ignorable missingness on the primary neurocognitive endpoint analysis will be conducted using the pattern mixture model approach as described below (see Appendix 10.6 for more details).

In the pattern-mixture model approach, different imputation strategies will be applied to the primary neurocognitive endpoint (i.e. CANTAB cognitive domain SWM strategy z-score change from baseline to Week 96) values missing during TEAE period (i.e. within the time period from the first double-blind IMP injection up to the day of the last double-blind injection +70 days) in contrast to those missing after the TEAE period. Presented below are the reasons for considering differences in the impact of alirocumab dependent on the timing of the last study treatment administration:

- Patients who discontinued study treatment due to adjudicated neurocognitive events but are still within the TEAE period would continue to show impact from treatment similar to that observed for other patients who also had adjudicated neurocognitive events.

Note: The neurocognitive events recorded on the AE eCRF by the investigator are defined below, by any of the following programmatical procedures:

- Sponsor neurocognitive events CMQ;
- FDA neurocognitive events CMQ;
- Investigator identified NC events, as entered in the eCRF.
- Patients who discontinued study treatment due to reasons other than adjudicated neurocognitive events but are still within the TEAE period would continue to show impact from treatment similar to that observed for patients without any adjudicated neurocognitive events.
- Patients who discontinued study treatment (alirocumab or placebo) but are after the TEAE period would no longer be impacted by study treatment, and thus would have SWMS values similar to patients receiving placebo.

Missing data from the primary safety population will be imputed 100 times to generate 100 complete data sets, using the approach described above. The 100 completed datasets of

observed and imputed LDL-C data will be used for primary neurocognitive endpoint analyses.

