10. APPENDIX

10.1. Summary of Statistical Analyses

Primary Neurocognitive Endpoint Analysis:

Endpoint	Analysis Populations	Statistical Method	Supportive Analysis	Subgroup Analysis	Other Analyses
Change from baseline to week 96 in SWM strategy z-score	Primary Safety Population	MMRM	Yes, including handling of missing data	Yes	1) Actual stratification factor 2) Multiple Imputations + ANCOVA 3) Pattern Mixture Model

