10.5. Detailed Description of the Multiple Imputation Procedure

The following is a detailed description of the multiple imputation procedure which will be used for sensitivity analysis of primary endpoint as well as the analysis of the secondary endpoints.

In general, the missing pattern is anticipated to be not monotone, a two-step approach will be used:

- Step 1: the MCMC method will be used in conjunction with the IMPUTE=MONOTONE option to create an imputed data set with a monotone missing pattern.

- Step 2: Using the monotone data set from step 1, missing data will be imputed using the regression method.

The imputation model for step 1 will include the treatment group and the values of the analyzed parameter at baseline and planned time-points up to week 96.

The imputation model for step 2 will include the same variables as in step 1 with the following additional variables:

- the randomization strata (age and statin use strata);
- age, BMI, and gender (age and BMI included as continuous variables).

Non-continuous variables included in the imputer's model (i.e., treatment group, randomization strata and gender) are not expected to be missing.

In addition, for continuous efficacy variables anticipated to have a non-normal distribution (i.e. TG and Lp(a)), data will be log-transformed before imputation process and then back-transformed to create the imputed data sets using the TRANSFORM statement of SAS MI procedure.

For variables other than those continuous efficacy variables anticipated to have a non-normal distribution (i.e. TG and Lp(a)), for each simulation leading to negative imputed value, another value will be redrawn using MINIMUM option of MI SAS procedure.

The number of imputations (100) will be informally verified by replicating sets of 100 imputations and checking whether the combined results are stable. If not stable, the number of imputations will be increased and informally checked as above, and thus continued until stable estimates are obtained.

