Missing SWMS values from the primary safety population will be imputed 100 times to generate 100 complete data sets. The change from baseline to Week 96 will be derived from observed and imputed SWMS at this time point. The completed data sets will be analyzed using an analysis of covariance (ANCOVA) model with treatment group and randomization strata as fixed effects, and the baseline SWMS value as continuous covariate. The results from the 100 analyses will be combined using Rubin’s formulae. If necessary, the number of imputations (100) will be increased until stable estimates are obtained.

Imputation Strategy 1: Missing data during the TEAE period for patients who discontinued study treatment due to adjudicated neurocognitive events

The imputation strategy for missing SWMS values following discontinuation of study treatment due to adjudicated neurocognitive events but still within the TEAE period, is to impute by patients who had at least one adjudicated neurocognitive event during the TEAE period.

Specifically, data collected during the TEAE period for patients who had at least one adjudicated neurocognitive event during the TEAE period will be used to impute missing data.

For each patient, missing SWMS values will be imputed 100 times, using a random draw from a normal distribution, with mean equal to the mean of the observed SWMS values, and variance equal to the conditional variance of observed SWMS values given the baseline value, at the specific time-point from patients in the same treatment group who had adjudicated neurocognitive events during the TEAE period.

Let Y_0 and Y_1 denote the SWMS at baseline and at the specific time-point respectively. Since Y_0 and Y_1 are assumed to have a bivariate normal distribution, the conditional variance of Y_1 given Y_0 is:

$$Var(Y_1|Y_0 = y_0) = \sigma_1^2(1 - \rho^2)$$

Where σ_1^2 denotes the variance of Y_1 and ρ the coefficient of correlation between Y_0 and Y_1 .

During the random generation process, a minimum value of 4 and a maximum of 28 will also be applied in order to avoid imputed SWMS values out of range.

Imputation Strategy 2: Imputation of missing data during the TEAE period for patients who discontinued study treatment due to reasons other than adjudicated neurocognitive events

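### The multiple-imputation check of the primary endpoint redraws valid negative z-scores and analyses a percent change of a z-score, so it cannot be read against the 0.2 margin

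*SAP*

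**What the plan says.** The primary endpoint in SAP 4.6.1 is an absolute change: "week 96 SWM strategy z-score minus the patient's baseline SWM strategy z-score". Each z-score subtracts the pooled baseline mean of both arms and divides by the pooled baseline SD; a lower score is better. SAP 5.6.1 tests this with an MMRM without imputation: "The upper CI limit will be compared to the noninferiority margin which is defined as 0.2".

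SAP 5.6.1.2 adds two missing-data re-analyses. In the first, multiple imputation followed by ANCOVA, the "percent change from baseline at week 96 will be then derived from observed and imputed SWM strategy z-score at this time point", with the baseline z-score as covariate. It refers to SAP 10.5 for the procedure. SAP 10.5 says that it serves the primary-endpoint sensitivity analysis as well as the secondary endpoints. Apart from TG and Lp(a), which are log-transformed, it sets this rule: "for each simulation leading to negative imputed value, another value will be redrawn using MINIMUM option of MI SAS procedure".

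Other parts of the SAP use absolute change. The table in 10.1 lists multiple imputation with ANCOVA in the row for "Change from baseline to week 96 in SWM strategy z-score". The pattern mixture model in 10.6 says "The change from baseline to Week 96 will be derived from observed and imputed SWMS at this time point" and limits its draws to 4 to 28.

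**The concern.** Neither rule fits a centred z-score. The floor at zero treats better-than-average performance as impossible, so every missing patient is imputed as worse than the baseline mean. The percent change has a divisor that is negative for about half of patients and close to zero for many, and its units are not those of the margin.

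The wording appears to come from a lipid analysis, where values are positive and percent change is usual. The same section says that "observed and imputed LDL-C data will be used for primary neurocognitive endpoint analyses", and it plots z-scores at weeks 8 and 12, when Protocol Table 1 schedules no neurocognitive battery.

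The stake is the robustness claim. The plan allows for 40% dropout, and this is one of only two re-analyses that address missing data. Followed literally, it can neither support nor question the MMRM.

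**Working it through.** **Inputs from the documents.** Margin 0.2, SD 1.0, assumed true difference 0, 1:1 allocation, 651 evaluable and 1085 randomised per arm, dropout of 20% then 25% (SAP 2.2 and 2.1). The power statement is "To achieve 95% power using a 2-sided 95% confidence interval (CI) approach (2-sided alpha=0.05".

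**Assumed, not in the documents.** Normal scores, no average drift in the placebo arm, correlation r between baseline and week 96 of 0.4 to 0.8, and week 96 imputed from treatment and baseline only.

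**The plan's own figure.** Normal approximation: 2 × (1.960 + 1.645)² / 0.2² = 649.7, so 650. The noncentral t gives 651 (power 0.9501). Dropout: 651 / (0.80 × 0.75) = 1085. Both figures reproduce, and neither depends on the imputation rules.

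**Floor at zero, closed form.** For a patient with baseline b and treatment shift d, the draw has mean μ = r·b + d and SD s = √(1 − r²). Redrawing negatives changes its mean to μ + s·φ(μ/s)/Φ(μ/s). Averaging over b:

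| r | mean imputed z, d = 0 (correct: 0) | gap between arms among imputed patients, d = 0.20 (correct: 0.20) |
|---|---|---|
| 0.4 | 0.750 | 0.080 |
| 0.6 | 0.687 | 0.083 |
| 0.8 | 0.587 | 0.091 |

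With d = 0, half of all draws are negative and are discarded.

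With the same fraction m missing in both arms, the estimate is 0.20·(1 − m) + m·gap. At r = 0.6:
- m = 10%: 0.180 + 0.0083 = 0.188
- m = 20%: 0.160 + 0.0167 = 0.177
- m = 40%: 0.120 + 0.0334 = 0.153

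At 40% missing the estimate is 0.152 for r = 0.4 and 0.156 for r = 0.8.

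If the arms differ in missingness and there is no true effect, the false difference is the imbalance times the mean imputed value. A 4-point imbalance gives 0.030/0.027/0.023 at r = 0.4/0.6/0.8, and a 10-point imbalance gives 0.075/0.069/0.059. The sign follows the arm with more missing data.

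**Floor, simulation with absolute change and Rubin's rules.** True harm 0.20, equal missingness. Entries are the share of trials whose upper limit falls below 0.2 (nominal 2.5%).

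| setting | 10% missing | 20% missing | 40% missing |
|---|---|---|---|
| floor, r = 0.4 | 5.0% | 7.8% | 22.5% |
| floor, r = 0.6 | 5.2% | 8.5% | 24.7% |
| floor, r = 0.8 | 5.5% | 10.8% | 30.3% |
| no floor, r = 0.6 | 1.3% | 2.3% | 2.2% |

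These used 1000 per arm, 600 trials and 25 imputations. A separate simulation (1085 per arm, 150 trials, 10 imputations, r = 0.5 and 0.7) gave 21–25% with the floor at 40% missing, against 4.0–4.7% without it. The floor also narrows the interval: at r = 0.5 and 40% missing, the standard error falls from 0.049 to 0.040.

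**Percent change, arithmetic.** The formula is 100 × (week 96 − baseline) / baseline. The same worsening of 0.2 is +20% at a baseline of 1, +200% at 0.1, −200% at −0.1 and −20% at −1. An improvement from −1.0 to −1.5 is 100 × (−0.5)/(−1.0) = +50%. For a standard normal baseline, 8.0% of patients lie within 0.1 of zero.

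**Percent change, simulation.** Complete data, r = 0.6, true harm 0.20, 1000 trials: the estimated difference had a 5th to 95th percentile range of −963 to +889 percentage points and was positive in 49.6% of trials. Its interval excluded zero in 2.6%. The ratio is heavy-tailed, and a repeat gave about −1250 to +1010, 51% and 1.3%. Analysed as absolute change, the same harm excludes zero in more than 99% of trials.

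**The case against.** The strongest reply is that raw scores were meant. SAP 10.5 refers only to the analysed parameter. The pattern mixture section also describes its endpoint as a z-score change, yet draws within 4 to 28, so a z-score label does not prove that z-scores are drawn. If raw scores are imputed, a minimum of zero almost never acts and the floor figures above disappear. That is fair as a guess at intent, but 5.6.1.2 says z-score and 10.5 does not say otherwise. The percent change remains on either reading.

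Second, the percent change is contradicted by 4.6.1 and 10.1, and the sentence after the LDL-C slip refers correctly to SWM strategy data. A careful programmer would probably choose absolute change. That choice would then be made outside the plan, which exists to fix it before unblinding.

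Third, the size of the percent-change spread depends on a continuous score. With an assumed integer score (SD 3 to 5), the range was about −22 to +24 up to −32 to +30 with a mean of 16.5, and −365 to +86 with a mean of 16.1 and SD 3. The interval excluded zero in 7% to 46% of trials. This stands: the percentiles above are illustrative. Percent change is unusable in both cases.

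Fourth, no decision rests on this analysis, and with equal missingness and no true difference the floor does not bias the difference. Both points are correct and limit the severity.

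**Conclusion.** The concern holds as stated. As written, the multiple-imputation analysis is invalid for the primary endpoint on two separate grounds, and either one alone breaks the comparison with 0.2. That conclusion follows from the text and from the definition of the z-score. Only the sizes depend on the assumed correlation, missingness and score distribution.

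With equal missingness the floor shrinks a real harm, which is the unsafe direction in a non-inferiority safety study. With unequal missingness it can push either way: with 45% missing on Praluent and 35% on placebo, a true 0.20 was estimated as 0.21–0.22.

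The scope is limited. The MMRM decision and the sample size do not use these rules, and the pattern mixture model has neither of them, although 10.6 does not say how its result is returned to the z-score scale. This should be fixed before database lock.

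**What to change.** - **SAP 5.6.1.2, multiple imputation:** replace the percent change with the absolute change from baseline in the SWM strategy z-score.
- **SAP 5.6.1.2, pattern mixture paragraph:** replace the reference to LDL-C data with SWM strategy data, and check the rest of the section for lipid wording, including the week 8 and 12 plots.
- **SAP 10.5:** restrict the non-negative redraw to lipid variables. State that SWM strategy is imputed either as a z-score with no minimum, or as a raw score within 4 to 28 that is then standardised with the same pooled baseline mean and SD. Either way the ANCOVA estimate is on the scale of the margin.

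In simulation, absolute z-score change without the floor recovered true differences of 0, 0.2 and 0.3 without material bias. The cost is SAP wording only. There is no effect on patients, data collection or the planned 1085 per arm.
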